### **6.1.3 Change in ART regimen**

Upon meeting eligibility criteria, individuals on protease inhibitor or NNRTI-based regimens, or regimens containing cobicistat will be switched to an integrase-inhibitor-based regimen (raltegravir or dolutegravir) that does not contain cobicistat. The change in ART regimen will occur at least 2 weeks prior to baseline leukapheresis (Visit 2, week - 2).

Study investigators will discuss changes in ART regimen with the participant's primary care physician.

### **6.1.4 Leukapheresis / Blood Draw visits**

Leukapheresis will be performed on day -14 and day 154 (12 weeks after completion of treatment cycle 2).

On leukapheresis visits, site personnel will:

- Answer any questions about the study;
- Perform leukapheresis;
- Obtain changes in concomitant medications;
- Assess weight, height and vital signs (pulse, respiratory rate, blood pressure and temperature);
- Perform a directed physical examination;
- Perform a pregnancy test for all female volunteers;
- Perform pregnancy avoidance counseling;
- Collect blood and urine specimens for all tests as indicated in the Time of Events Schedule (Appendix A);
- Assess the occurrence of any adverse events;

Leukapheresis samples will be used for viral outgrowth assay and other research assays.

### **6.1.5 Treatment Cycles 1 and 2**

3BNC117 infusion visits (days 0 and 56 for Group A only)

Prior to drug infusion, site personnel will:

- Answer any questions about the study;
- Review interim medical history (including concomitant medications);
- Review safety laboratory data;
- Perform a physical examination including weight, vital signs (pulse, respiratory rate, blood pressure and temperature) and any further examination indicated by history or observation;
- Collect blood and urine specimens for all tests as indicated in the Time of Events Schedule (Appendix A);
- Perform pregnancy and safe sex counseling;
- Perform a pregnancy test for all pre-menopausal female volunteers and obtain results prior to drug infusion;
- Perform baseline assessment and record any systemic symptoms;
- 3BNC117 will be prepared for administration according to the Site Pharmacy Standard Operating Procedures;
- 3BNC117 mAb will be administered via a peripheral vein by slow intravenous infusion.
- The infusion will take approximately 60 minutes.
- Subjects will be observed for adverse reactions at the study site for 1 hour after end of infusion. Presence or absence of adverse events will be recorded at 1 hour post infusion.
- Vital signs (pulse, respiratory rate, blood pressure and temperature) will be monitored at the end of infusion, 30 (+/- 5 min) minutes, and 1 hr (+/- 5 min) post infusion.
- If volunteers develop acute infusion reaction during 3BNC117 administration, the infusion will be held. Rescue medications, including acetaminophen, diphenhydramine and glucocorticoids will be available in the RUH, AUH or UCH infusion unit for use if clinically indicated. Infusion may be reinitiated after symptoms improve, and the remaining dose will be administered over 3 hours.

Romidepsin infusion visits (days 2, 9, 16, 58, 65, and 72 for Group A; days 0, 7, 14, 56, 63, and 70 for Group B)

Prior to drug infusion, site personnel will:

- Answer any questions about the study;
- Review interim medical history (including concomitant medications);
- Review safety laboratory data, including electrolytes;
- Perform a physical examination including weight, vital signs (pulse, respiratory rate, blood pressure and temperature), and any further examination indicated by history or observation;
- Collect blood and urine specimens for all tests as indicated in the Time of Events Schedule (Appendix A);
- Perform pregnancy and safe sex counseling;

- Perform a pregnancy test for all pre-menopausal female volunteers (blood will be sent STAT) and obtain results prior to drug infusion;
- Perform baseline assessment and record any systemic symptoms;
- Participants will be administered prophylactic ondansetron 8 mg, orally (PO), approximately 30 minutes prior to starting the infusion.
- Additional details regarding romidepsin administration are described below in Section 6.2.4
- If volunteers develop acute infusion reaction during romidepsin administration, the infusion will be held. Rescue medications, including acetaminophen, diphenhydramine and glucocorticoids will be available at the site infusion unit for use if clinically indicated. Infusion may be reinitiated after symptoms improve as per Appendix D.

Post-infusion follow up visits (days 3, 10, 12, 17, 23, 30, 59, 66, 68, 73, 75, 82 for Group A; days 1, 8, 10, 15, 21, 28, 57, 64, 66, 71, 73, 80 for Group B).

After romidepsin infusions, follow up visits will be performed two to three times a week (see the Time of Events Schedule, Appendix A).

On these visits, site personnel will:

- Answer any questions about the study;
- Review interim medical history (including concomitant medications);
- Review safety laboratory data;
- Perform a directed physical examination including vital signs (pulse, respiratory rate, blood pressure and temperature), and any further examination indicated by history or observation;
- On the visits that occur the day following romidepsin infusion, an ECG will be performed;
- Collect blood and urine specimens for all tests as indicated in the Time of Events Schedule (Appendix A);
- Assess the occurrence of any adverse events;

Specific procedures to be performed at each clinic visit are illustrated in the Time of Events Schedule (Appendix A).

Contact only visit (day 119 for Group A, day 119 for Group B)

Six weeks after the conclusion of the second treatment cycle, participants will be contacted by phone or email to assess for any changes to their medication or adverse events.

#### **6.1.6 Analytical treatment interruption**

During ART interruption follow up visits will be performed on a weekly basis (Appendix A, Time of Events Schedule).

- Answer any questions about the study;

- Review of interim medical history and use of concomitant medications;
- Assessment of adverse events;
- Pregnancy counseling (monthly) and pregnancy testing (every 2 weeks);
- Review of safety laboratory data (monthly);
- Directed physical examination including weight, vital signs (pulse, respiratory rate, blood pressure and temperature), and any further examination indicated by history or observation;
- Collection of blood and urine specimens for all tests as indicated in the Time of Events Schedule (Appendix A);
- In case of adverse event(s), the volunteer will be assessed and followed up by the clinical team. Supplemental visit(s) for further investigation can be planned at the discretion of the principal investigator or designee. Supplemental visit(s) may be recommended if clinically indicated or to clarify observations. Any abnormalities (adverse events) attributed to study drug, including laboratory abnormalities, should be subsequently followed until the event or its sequelae resolve or stabilize.

#### **6.1.7 ART interruption and re-initiation of combination ART**

ART regimen will be discontinued at week 24, 16 weeks after the second 3BNC117 infusion. ART will be discontinued for 12 weeks and if viral rebound does not occur, subjects can remain off ART with continued follow up.

At week 36, if a subject's HIV-1 VL remains undetectable, the subject will have the option to restart ART at that time or to continue weekly follow up through the end of the study (week 48). During the ATI, ART will be resumed if plasma HIV-1 RNA level  $\geq$  200 copies/ml in 2 consecutive measurements or if CD4+ count drops  $<$  350 cells/ $\mu$ l and the result is confirmed upon repeat measurement. In this case repeat measurements are performed at the next scheduled visit. If the HIV-1 RNA level is found to be  $\geq$  1000 copies/ml the subject will be contacted to return to clinic as soon as the result becomes available. Upon viral rebound, viral genotyping will be performed to determine if any resistance mutations are present. ART will also be reinitiated if the participant becomes pregnant, or if otherwise clinically indicated.

Subjects who experience viral rebound during the ATI will be followed on a modified schedule (Appendix B). These subjects will have study visits every 2 weeks until their HIV-1 VL is undetectable on 2 consecutive measurements. At that point, they will be followed every 8 weeks until the final visit at week 48.

Subjects' primary care physicians will be contacted when virologic rebound occurs and periodically throughout the study.

During ATI phase of the study subjects may be at increased risk of transmitting HIV to their partners and of HIV-1 superinfection from an HIV-infected partner. Therefore, subjects will be asked to use male or female condoms for the duration of ART interruption. In the event of a high-risk exposure to an HIV-infected partner, a subject may re-initiate ART as clinically indicated by his/her HIV primary care physician.

### **6.1.8 Final Visit/Early Termination Visit**

Assessments will be undertaken according to the Time of Events Schedule (Appendix A).

### **6.1.9 Long term safety follow up (Years 2 and 3)**

Volunteers will be contacted by telephone or email 2 and 3 years after last romidepsin infusion to collect information regarding new health concerns, diagnoses, hospitalizations, or congenital abnormalities.

### **6.1.10 Discontinuation of 3BNC117 infusion and/or volunteer withdrawal from study**

#### **6.1.10.1 Discontinuation of 3BNC117 infusion**

The 3BNC117 infusion will be discontinued for any of the following reasons:

1. Any immediate hypersensitivity reaction (such as urticarial rash; bronchospasm; laryngeal edema; anaphylaxis; syncope).
2. Life threatening medical event during 3BNC117 infusion.

#### **6.1.10.2 Discontinuation from subsequent 3BNC117 infusion**

Volunteers will be discontinued from second 3BNC117 infusion for any of the following reasons:

1. A disease or condition or an adverse event that may develop, regardless of relationship to 3BNC117, if the principal investigator or designee is of the opinion that another 3BNC117 infusion will jeopardize the safety of the volunteer.
2. Any immediate hypersensitivity reaction (such as urticarial rash; bronchospasm; laryngeal edema; anaphylaxis; syncope).
3. Life threatening medical event following 3BNC117 unless not related to the investigational product.
4. Intercurrent use of immunosuppressive medication considered significant by the trial physician (e.g., systemic corticosteroids).
5. Pregnancy.
6. Subject's request to discontinue further 3BNC117 infusions.
7. ALT or AST increases of or exceeding 3 x the upper limit of normal with concurrent increase in total bilirubin of or exceeding 2 x the upper limit of normal.

#### **6.1.10.3 Discontinuation of Romidepsin infusion**

The romidepsin infusion will be discontinued for any of the following reasons:

1. Any immediate hypersensitivity reaction (such as urticarial rash; bronchospasm; laryngeal edema; anaphylaxis; syncope).
2. Life threatening medical event during romidepsin infusion.

#### **6.1.10.4 Discontinuation from subsequent Romidepsin infusions and Romidepsin dosing modification**

Participants should continue to receive therapy until they complete the planned infusions or study treatment is not tolerated. If study drug-related toxicities are observed, treatment can be resumed only if these toxicities have returned to baseline level or their severity decreased to  $\leq$  grade 1 according to the Common Terminology Criteria for Adverse Events v.4.03 (CTCAE) for infusion-related toxicity and the DAIDS Table for Grading the Severity of Adult and Pediatric Adverse Events, Version 2.0 for non-infusion-related toxicity. Discontinuation from subsequent romidepsin infusions will occur for the following reasons:

1. Grade 3 or 4 adverse events deemed related to romidepsin. Review by the protocol safety review team (PSRT) and the safety monitoring committee (SMC) will occur to determine if romidepsin may be restarted at a reduced dose. Guidelines for romidepsin dose reduction are provided in Appendix D.
2. A second occurrence of a grade 3 abnormality of ALT, AST, total bilirubin, ANC, platelet count, or hemoglobin.
3. Grade 4 abnormalities of ANC, platelet count, or hemoglobin. A review by the PSRT and SMC will occur to determine if a study pause is required.
4. ALT or AST increases of or exceeding 3 x the upper limit of normal with concurrent increase in total bilirubin of or exceeding 2 x the upper limit of normal. In this instance, discontinuation of 3BNC117 will occur as well. A review by the PSRT and SMC will occur to determine if a study pause is required.

The dose of romidepsin may be modified for a participant (Appendix D). 3BNC117 dose modification is not allowed.

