#### **6.1.10.5 Withdrawal from the study (Early Termination)**

Volunteers may be withdrawn from the study permanently for the following reasons:

1. Volunteers may withdraw from the study at any time if they wish to do so, for any reason.
2. Following an adverse event at the discretion of the investigator (or designee).
3. Request of the primary care provider if s/he thinks the study is no longer in the best interest of the subject.
4. Subject judged by the investigator to be at significant risk of failing to comply with the protocol in a manner that might lead to harm to self or seriously interfere with the validity of the study results.
5. At the discretion of the FDA, Danish Health Authority, the PEI, the BfArm or investigator.

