##### **15.1 Protocol Safety Review Team**

The Protocol Safety Review Team (PSRT) will include the available site PIs and co-investigators. Additional members could include senior clinical research nursing staff and site staff. The PSRT will meet on a weekly basis to review any adverse events; minutes will be recorded. For any AE Grade 3 or above deemed possibly, probably or definitely related to 3BNC117 and/or romidepsin, the site PI will notify the PSRT within 24 hours and the PSRT will convene within 1 business day to review these AEs. The PSRT will decide by consensus whether AEs should also be reviewed by the SMC.

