All available safety data will be reviewed by the SMC three weeks after the first five participants receive the second 3BNC117 infusion, and every 6 months thereafter. The study will not pause, but following the review, SMC member(s) will make a recommendation to the principal investigator(s) regarding the continuation of the trial.

SAEs and unanticipated adverse events will be reported to the SMC within 2 working days of the site becoming aware of the event. If there is one grade 4 SAE judged as possibly, probably or definitely related to the administration of 3BNC117 or romidepsin by the principal investigator or designee, no additional enrollment will take place pending a review by at least two members of the SMC. Following this review, the SMC member(s) will make a recommendation to the principal investigator regarding the continuation of the trial.

All updated versions of the protocol will be provided to the SMC members. The review of trial data by the SMC will take place at least every 6 months. For these reviews, the study team will provide the SMC with updated records of all adverse events (AEs) of a grade 2 or greater toxicity.

The SMC will provide a written report to the sponsor at the RU and the site PIs after each evaluation. The PIs will, in turn, distribute these reports to the study team, the local IRBs and the FDA.

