**Table 1 Adverse events that may lead to a safety pause**

Event and relationship to study product	Severity	Occurrence	Action
SAE, related	Grade 3 or 4	First	Immediate pause until PSRT and SMC determination to resume enrollment
AE  , related	Grade 3 or 4 	Second 	Immediate pause until PSRT and SMC determination to resume enrollment
ALT or AST increase > 3 x ULN with concurrent increase in total bilirubin > 2 x ULN, any relatedness	N/A	First	PSRT and SMC review to consider pause
Abnormality of ANC, platelet count, or hemoglobin, any relatedness	Grade 4	First	PSRT and SMC review to consider pause
AE  , related	Grade 3 or 4 	First	PSRT review within 1 business day to consider pause

 Does not include subjective solicited symptoms (fatigue/malaise, myalgia, arthralgia, chills, headache, nausea).

 If no evidence of disease is present other than an abnormal laboratory value, the test must be repeated at least one time.

 PSRT and SMC will determine whether the reported related AE (Grade 3 or 4) is a second occurrence of a previously reported AE (Grade 3 or 4).

If a study pause is triggered, all enrollment and infusions will be held until review by the PSRT or SMC. Resumption of enrollment and study treatment may be determined by the PSRT or SMC (in consultation with the FDA, if required) following a cumulative review of the available safety data as outlined in the charter. If a decision to resume study enrollment and study treatment administration is made, the PSRT and/or SMC will record its judgment. As needed, the appropriate regulatory authorities will be informed in writing of the decision by the PSRT and/or SMC to resume or discontinue study activities. Sites are responsible for notifying their IRBs according to local standards and regulations.

Volunteers will be withdrawn from the study if: a) the study team feels that continued participation in the study would be harmful to the health of a subject; b) if the study volunteer fails to comply with the study procedures and/or fails to keep study visit

appointments; c) The RU, AU or UC IRBs decided to stop or cancel the study for any reason.

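### In the visible text of 6.1.10.4, a repeat grade 3 liver value of any cause stops romidepsin, but a first isolated grade 4 value judged unrelated does not (minor safety inconsistency)

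*Combined protocol and SAP*

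**What the plan says.** Section 6.1.10.4 gives four grounds for withholding later romidepsin infusions:

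- Item 1: a grade 3 or 4 adverse event attributed to romidepsin.
- Item 2: "A second occurrence of a grade 3 abnormality of ALT, AST, total bilirubin, ANC, platelet count, or hemoglobin". It sets no condition on cause.
- Item 3: "Grade 4 abnormalities of ANC, platelet count, or hemoglobin". It also sets no condition on cause, and adds a review by the protocol safety review team (PSRT) and the safety monitoring committee (SMC) on whether to pause the study.
- Item 4: ALT or AST at 3 x ULN or more together with total bilirubin at 2 x ULN or more.

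If none of these is met, the same section has participants carry on to the end of the planned infusions unless treatment is not tolerated. Its requirement that toxicity return to baseline or to grade 1 or less before dosing resumes is limited to toxicity related to study drug.

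Table 1 in section 15.8 repeats the pattern for pausing the trial. Its grade 4 laboratory row reads "Abnormality of ANC, platelet count, or hemoglobin, any relatedness".

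**The concern.** A stop list should become stricter as severity rises. For ANC, platelets and hemoglobin this one does: a second grade 3 value stops romidepsin, and a first grade 4 value stops it and goes to both committees. For ALT, AST and total bilirubin the rule that ignores cause ends at grade 3. The milder repeat value is a required stop, and the more severe first value is not.

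The plan elsewhere treats liver values as important. Item 2 lists them without asking about cause, and exclusion criterion 16 bars entry at ALT or AST of 1.25 x ULN or more, or bilirubin above ULN. The omission from item 3 therefore looks unintended.

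What is at stake is participant safety between infusions. In an open-label trial at three sites, whether a grade 4 liver value is a required stop would depend on one attribution. The plan avoids that dependence for blood counts and for repeat grade 3 values. The statistical analysis is not affected.

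**Working it through.** The plan gives no figure to reproduce. The check sets two cases against every visible rule.

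Case A is a second isolated grade 3 ALT, AST or bilirubin, judged unrelated. Case B is a first isolated grade 4 ALT, AST or bilirubin, judged unrelated.

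| Rule | Case A | Case B |
|---|---|---|
| 6.1.10.3 (hypersensitivity, or a life-threatening event during infusion) | no | no |
| 6.1.10.4 item 1 (related grade 3 or 4) | no | no |
| 6.1.10.4 item 2 (second grade 3, six analytes) | **stop** | no |
| 6.1.10.4 item 3 (grade 4, three blood counts) | no | no |
| 6.1.10.4 item 4 (combined liver rise) | no | no |

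Reading item 2 as grade 3 or higher does not help Case B, because a second occurrence is still needed.

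**Table 1 for Case B.** There are 5 rows. Three require relatedness. The other two apply whatever the attribution, but one needs ALT or AST and bilirubin raised together and the other covers the three blood counts. Rows met: 0 of 5.

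**Analyte count.** Item 2 names 6 analytes and item 3 names 3. Without a grade 4 rule that ignores cause: 6 − 3 = 3 (ALT, AST, total bilirubin).

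**Time at risk.** Section 7.1 gives the romidepsin days.

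- Group A (2, 9, 16, 58, 65, 72): gaps 7 + 7 + 42 + 7 + 7 = 70 days.
- Group B (0, 7, 14, 56, 63, 70): gaps 7 + 7 + 42 + 7 + 7 = 70 days.

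After day 72 or day 70 no romidepsin remains to be stopped.

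**Frequency.** The documents give no rate for unrelated grade 4 liver values, and none is assumed here. Section 3.1.3.2 offers only indirect evidence. In the six-person romidepsin pilot, all 35 related events were grade 1; the grades of the other 41 − 35 = 6 events are not stated. In the vaccine-plus-romidepsin trial, 96% of 141 events were grade 1, which leaves 0.04 × 141 = 5.64, about 6 events of any type above grade 1, and no clinically significant biochemistry effects were reported. This suggests that such values are uncommon but does not estimate how often they occur.

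**The case against.** Four points on the other side carry weight.

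- **Unseen text.** Section 6.1.10.4 sends dose changes to Appendix D, and section 15.8 cites a charter. Neither is available, and a liver limit by grade could well sit in Appendix D. This stands, and it limits the point to the visible text.
- **A narrow case.** Four conditions must hold together: first occurrence, isolated, grade 4, judged unrelated. A related event meets item 1, and a combined rise meets item 4 and a Table 1 row. Sections 15.1 and 15.2 count a possible relation as related when escalating, so an unexplained grade 4 liver value between infusions would be hard to leave out. This stands. What remains is mainly events with a clear other cause.
- **Existing safeguards.** Section 6.1.5 requires review of safety laboratory data before each romidepsin infusion. Section 15.1 states: "The PSRT will meet on a weekly basis to review any adverse events; minutes will be recorded". Within a cycle the next infusion is 7 days away, so that meeting would normally see the value first. Section 15.2 adds: "SAEs and unanticipated adverse events will be reported to the SMC within 2 working days of the site becoming aware of the event". Section 15.8 makes withdrawal mandatory once "the study team feels that continued participation in the study would be harmful to the health of a subject". Section 6.2.11 requires a work-up for any graded bilirubin rise and allows hepatology referral on clinical grounds. All this stands. But each route either depends on judgement or sets no romidepsin stop, and the 6.2.11 work-up is not triggered by ALT or AST alone.
- **A reason to single out blood counts.** Section 3.1.3.2 reports the common grade 3/4 romidepsin events as haematologic plus fatigue. This explains item 3 on its own, but not why liver values appear in item 2 and then drop out.

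A reader might infer that a participant with a grade 4 liver value would simply be dosed again, or that the protocol has no liver stopping rule. The documents support neither: items 1, 2 and 4 are liver stops, and the safeguards above apply to the remaining case.

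**Conclusion.** The inconsistency is real but minor. In the visible text of 6.1.10.4, a first isolated grade 4 ALT, AST or total bilirubin judged unrelated has no required romidepsin stop, while a second grade 3 value in the same analyte does. It concerns 3 of the 6 analytes in item 2 and can affect dosing only within a 70-day span in each arm.

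The conclusion rests on two assumptions: that the items are read as written, and that Appendix D sets no such limit. If Appendix D does set one, all that remains is a missing cross-reference in item 3. The frequency of the event is unknown and probably low. The primary endpoint and its analysis are unaffected.

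A reader might also take the absence of a matching Table 1 row as a defect of the same kind. That goes too far. Table 1 governs pausing the whole trial, and sending one participant's unrelated liver value to a pause review is a matter of preference.

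**What to change.** Extend item 3 of 6.1.10.4 so that a grade 4 ALT, AST or total bilirubin, whatever the attribution, stops further romidepsin, as a grade 4 blood count already does. If Appendix D already contains a liver limit, align item 3 with it and cross-refer.

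Item 3 carries a second sentence that requires a study-pause review. The sponsor should say whether that sentence is meant to cover the added liver values or only the blood counts. Adding the liver values to the grade 4 row of Table 1 is optional and should follow the same decision.

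The cost is a small wording change, with no new tests or visits. The downside is that a participant whose grade 4 liver value has another cause would occasionally lose the remaining romidepsin doses.
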